6.8 CONCOMITANT THERAPY

Any medication or vaccine (including over-the-counter or prescription medicines, vitamins and/or herbal supplements, or other specific categories of interest) or procedures that the participant is receiving at the time of enrollment or receives during the study must be recorded along with:

- Reason for use
- Dates of administration, including start and end dates
- Dosage information, including dose and frequency

The Medical Monitor should be contacted if there are any questions regarding concomitant or prior therapy.

Prohibited medications

The following concomitant treatments are not permitted during the Screening Period and throughout the study unless otherwise specified:

- Intranasal corticosteroids within 5 half-lives or at least 30 days, whichever is longer, before Visit 1, during the Screening Period, and up to Week 52 (however, INCS can be used for other coexisting diseases [eg, allergic rhinitis] after Week 24, as needed, to keep more participants for the assessment of exploratory endpoints with 52-week treatment)

- Any systemic immunosuppressive treatment, including but not limited to methotrexate, cyclosporine, mycophenolate, tacrolimus, gold, penicillamine, sulfasalazine, hydroxychloroquine, azathioprine, and cyclophosphamide, within 4 weeks before Visit 1 or 5 half-lives, whichever is longer, during the Screening Period, and up to Week 52
- Anti-IgE therapy (omalizumab) within 4 months before Visit 1, during the Screening Period, and up to Week 52 and other biologics for immuno-inflammatory conditions within 4 weeks before Visit 1 or 5 half-lives, whichever is longer, and up to Week 52
- Allergen immunotherapy during the Screening Period and up to Week 52 (except if initiated more than 3 months prior to Visit 1 and dose stable for 1 month prior to Visit 1)
- Long-term courses (>2 weeks) of SCS are prohibited from Visit 1 onward
- Short-term courses (≤ 2 weeks) of SCS are prohibited only during the Screening Period, and they are allowed as rescue medication after Visit 2
- Live, attenuated vaccines within 4 weeks before Visit 1, during the Screening Period, and up to Week 52 (Appendix 8 [[Section 10.8](#)])
- Systemic antibiotic for >2 weeks during the study
- Use of intranasal decongestants, except for preparation of nasal endoscopy (NE)

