## 2 SAMPLE SIZE DETERMINATION

The EFC14280 study, which was conducted as a pivotal study for Nasal Polyposis, the proportion of responders (NPS improvement from baseline  $\geq 1$ ) at Week 24 was 62.0% in the dupilumab group. Based on this result, the target proportion of responders (NPS improvement from baseline  $\geq 1$ ) at Week 24 in this postmarketing study is at least 50.0% to reflect the similar effect size between EFC14280 and this study.

It is necessary for 20 participants to achieve this response rate (at least 50%) with a 90% probability of success. The sample size was adjusted up to 25 to account for a 20% drop-out rate.

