**Table 4 - Populations for analyses**

Population	Description
Screened	All participants who signed the informed consent form (ICF).
Enrolled	The enrolled population includes all participants with a treatment kit number allocated and recorded in the interactive response technology (IRT) database, regardless of whether the treatment kit was used or not. Participants treated without a treatment kit number being allocated will not be considered enrolled and will not be included in any efficacy population.
Intent-to-treat (ITT)	Enrolled population with chronic rhinosinusitis with nasal polyposis (CRSwNP)
Modified ITT (mITT)	All participants in ITT allocated to study intervention administered at least 1 dose of study intervention
Per-protocol (PP)	All participants in mITT allocated to study intervention administered at least 1 dose of study intervention, and who did not receive intranasal corticosteroids (INCS) up to Week 24
Per protocol with extension term (PPE)	All participants in mITT allocated to study intervention administered at least 1 dose of study intervention during the intervention period after Week 24, and who did not receive INCS throughout the study
Safety (SAF)	All participants allocated to study intervention administered at least 1 dose of study intervention before Week 24
Safety for extension term (SAFE)	All participants allocated to study intervention administered at least 1 dose of study intervention during the intervention period after Week 24
Population without trial impact (disruption) due to COVID-19	A Population without trial impact (disruption) due to COVID-19 is defined as any participant in randomized population: - without any critical or major deviation related to COVID-19 - and who didn't permanently discontinue treatment due to COVID-19 - and who didn't permanently discontinue study due to COVID-19.

Abbreviations: CRSwNP: chronic rhinosinusitis with nasal polyposis; ICF: informed consent form; INCS: intranasal corticosteroids; IRT: interactive response technology; ITT: intent-to-treat; mITT: modified ITT; PP: per protocol; PPE: per protocol with extension term; SAF: safety; SAFE: safety for extension term

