## **4.5.2 Main Analytical approach**

### **4.5.2.1 Proportion of participants with NPS improvement from baseline $\geq 1$ at Week 52**

The number of participants and percentage with the 95% continuity corrected Wilson confidence interval (CI) will be provided at Week 52 in the PPE analysis population, similar to the primary endpoint (Estimand 1).

Participants who are rescued (undergo surgery for NP or receive SCS for any reason) will be considered nonresponders for time points after rescue. Participants who have missing data at Week 52 will be considered nonresponders.

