### **4.5.2.3 Same as primary and secondary endpoints**

Primary and secondary endpoints up to Week 24 will be summarized each visit. These endpoints after Week 24 up to Week 52 will be summarized each visit by dose regimen group and overall. Imputation will not be used.

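### The only Week 52 responder rate with nonresponder imputation is in PPE, which leaves out participants who stopped before the extension, so it tends to read high as a 52-week result from baseline

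*SAP*

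**What the plan says.** SAP Table 4 (and Protocol Table 5, in the same terms) restricts PPE to mITT participants with at least one dose "during the intervention period after Week 24, and who did not receive INCS throughout the study". SAP 4.5.2.1 gives the Week 52 responder proportion in PPE with a continuity-corrected Wilson interval. Participants with nasal polyp surgery or systemic corticosteroids (SCS) are nonresponders afterwards, and "Participants who have missing data at Week 52 will be considered nonresponders". SAP Table 3 names the same population and rules for this endpoint.

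Other Week 52 output exists. SAP 4.1 asks for by-visit tables of efficacy variables, including those after Week 24, in PP and mITT. For by-visit summaries SAP 4.5.2.3 says "Imputation will not be used", and SAP 5.4.4 leaves participants with missing categorical data out of percentages unless otherwise specified. SAP 3 adds a general sentence on supportive mITT analyses that names no Week 52 endpoint or rule. At Week 24, by contrast, Table 3 and SAP 4.3.4 set out an mITT responder analysis with its own handling of intercurrent events.

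Protocol 6.8 permits INCS after Week 24 for other coexisting diseases, with the stated purpose "to keep more participants for the assessment of exploratory endpoints with 52-week treatment".

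**The concern.** The exploratory objective concerns 52 weeks of treatment, and Protocol 4.1 describes the long-term aim as starting from the initial 24-week regimen. A participant who stops in the first 24 weeks belongs to that question. Under Protocol 6.8.1 surgery ends study treatment, and under Protocol 6.8 INCS use before Week 24 does so too. These participants, and those who stop early for lack of efficacy or an adverse event, cannot meet the PPE dosing condition. The nonresponder rule looks conservative, but it works only on those who reached the extension.

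The PPE condition on INCS raises a second matter. The protocol relaxes the INCS restriction to retain participants for the Week 52 endpoints, and PPE then removes those who use it from the main analysis of those endpoints.

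At stake is how the Week 52 rate is read. A figure conditional on reaching the extension could be quoted as the 52-week response to monotherapy.

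**Working it through.** **The plan's own figure.** Inputs are from SAP 2: reference rate 62.0% ("at Week 24 was 62.0% in the dupilumab group"), 20 evaluable participants, target of at least 50%, 90% probability. Exact binomial: P(X ≥ 10 | n = 20, p = 0.62) = 0.9077, which agrees with the stated 90%. Enrolment: 20 / (1 − 0.20) = 25, which agrees with "The sample size was adjusted up to 25 to account for a 20% drop-out rate". This calculation is for Week 24; the documents give no Week 52 response rate and no timing for drop-out.

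**Effect of the exclusion.** Assume all 25 are dosed. Let k be the number outside PPE, x the Week 52 responders inside PPE, and r the responders among the k.

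- PPE rate = x / (25 − k)
- All-treated rate = (x + r) / 25
- If r = 0, the ratio of the two is 25 / (25 − k): 25/24 = 1.04 for k = 1, and 25/20 = 1.25 for k = 5.

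The values of x are illustrative: 62% of 24 is 14.9 (take 15), 62% of 20 is 12.4 (take 12), and 15 of 20 serves as a higher case. Intervals are continuity-corrected Wilson, and r = 0 throughout.

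| k | PPE | All 25 | Gap (points) | Share of nonresponders outside PPE |
|---|---|---|---|---|
| 1 | 15/24 = 62.5% (40.8–80.4) | 15/25 = 60.0% (38.9–78.2) | 2.5 | 1/(1+9) = 10% |
| 5 | 12/20 = 60.0% (36.4–80.0) | 12/25 = 48.0% (28.3–68.2) | 12.0 | 5/(5+8) = 38% |
| 5 | 15/20 = 75.0% (50.6–90.4) | 15/25 = 60.0% (38.9–78.2) | 15.0 | 5/(5+5) = 50% |

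**When the gap closes.** It vanishes if the excluded respond at the PPE rate. With k = 5, x = 12 and r = 3, the all-treated rate is 15/25 = 60%, equal to 12/20. The bias is upward whenever the excluded do worse than those in PPE. That is likely for early stoppers. Protocol 7.1.1 has them assessed as soon as possible after stopping, and SAP Table 10 assigns only endoscopies from Day 322 onward to Week 52. Without a later endoscopy they are missing at Week 52, and so nonresponders under the plan's rule.

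**INCS users after Week 24.** Suppose 20 reach the extension, 4 of them use INCS, and PPE shows 10/16 = 62.5%. Keeping the 4 with their observed outcomes gives between 10/20 = 50% (none respond) and 14/20 = 70% (all respond). Dropping them can therefore raise or lower the rate.

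**The case against.** The best defence has four parts.

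- **The Week 52 objective is limited to participants not using INCS and refers to different dosing regimens.** Regimen groups exist only for those dosed after Week 24 (SAP 4.1). This stands as a reason to keep PPE, but it does not supply the rate from baseline.
- **Other output covers Week 52.** A reader might infer that Week 52 response is examined in PPE alone. It is not: SAP 4.1 provides PP and mITT by-visit tables, and since PP excludes only INCS up to Week 24, later INCS users stay in them. But SAP 4.5.2.3 rules out imputation. It names no population, so applying it to these tables is an inference, though the natural one. Early stoppers without a Week 52 reading then drop out of those percentages too.
- **The exclusions are visible.** SAP 4.2 reports population counts, Week 24 non-completers and their main reasons, with enrolled participants as denominator, so a careful reader could divide PPE responders by 25. That softens the problem but leaves the calculation and its interval to the reader.
- **The endpoint is exploratory**, no hypothesis is tested (SAP 4.6), and there is no Week 52 target. This stands and limits the importance of the point.

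A reader might also infer that PPE misses most treatment failures. The documents do not support that. Surgery after Week 24, SCS use and missing Week 52 data all count as nonresponse inside PPE. Protocol 6.8.1 keeps SCS-rescued participants on treatment unless the investigator withdraws it, so even those rescued before Week 24 can enter PPE. In the illustrations above, the share outside is 10% to 50%. Nor is INCS for a coexisting disease a failure of polyp treatment.

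**Conclusion.** The point holds as a limited one. The only Week 52 responder proportion with nonresponder imputation and an interval conditions on a dose after Week 24, and no Week 52 counterpart to the Week 24 mITT analysis is specified. As a 52-week rate from baseline it tends to be biased upward.

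The size cannot be derived from the documents. The range of 2.5 to 15 points rests on assumed responder counts, all 25 being dosed, and every excluded participant being a nonresponder. The upper part further requires the whole 20% drop-out allowance to fall before the extension. A flat 15-point overstatement, which a reader might take from the last row of the table, is therefore one unfavourable case and not an estimate. The exclusion of permitted INCS users sits awkwardly with the protocol's reason for permitting them, but its direction of bias is unknown.

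**What to change.** Add one Week 52 responder table in mITT, mirroring the Week 24 mITT supplementary analysis and using rules the plan already has:

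- nasal polyp surgery, SCS or missing Week 52 data count as nonresponse;
- data observed after treatment discontinuation are used, so stopping treatment is not by itself nonresponse (SAP 4.3.2 does not treat it so for the primary endpoint);
- INCS for CRSwNP counts as nonresponse, extending the Week 24 mITT rule to Week 52;
- participants using permitted INCS for a coexisting disease after Week 24 are kept with their observed data.

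State the scope of SCS explicitly: SAP 4.5.2.1 counts SCS for any reason, while the Week 24 mITT row of Table 3 adds a CRSwNP qualifier. Following 4.5.2.1 would keep the two Week 52 results comparable.

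Report the table beside the PPE result, with the number excluded from PPE and the reasons, separating early stopping from INCS use. Protocol 6.8 already requires the reason for each concomitant medication to be recorded, so INCS can be classified by indication.

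The cost is one extra table and a possibly less favourable rate. No new assessment is needed.

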## 4 STATISTICAL ANALYSES

The database lock will be performed when all participants have completed their treatment phase. Final analyses in the clinical study report will be based on all data collected up to this database lock.

### 4.1 GENERAL CONSIDERATIONS

The baseline value of efficacy parameters is defined as the last available value up to enrollment (Visit 2) but prior to the first dose of study medication unless otherwise specified. The baseline value of safety parameters is defined as the last available value prior to the first dose of investigational medicinal product (IMP). The baseline value of the other parameters is defined as the last available value prior to the first dose of IMP if the patient is treated, or the last available value up to enrollment if the patient is not exposed to IMP.

During the treatment term, including efficacy variables after Week 24, continuous variables and binary variables for efficacy by each visit will be summarized using descriptive statistics and frequency tables in the PP and mITT populations. Analyses up to Week 52 will be run using the PPE population, including data through Week 24.

All safety analyses up to Week 24 will be analyzed for the SAF analysis population. Safety data collected during the extension term after Week 24 up to Week 52 will be reported for the SAFE analysis population. Safety analyses for the extension term will be presented by dose regimen group and overall.

#### *Observation period*

The observation period will be divided into 2 segments:

- The **pre-treatment period** is defined as the period up to first IMP administration.
- The **treatment-emergent period** is defined as the period from the first IMP administration to the last visit in the study or the date of treatment discontinuation if discontinued from the study, whichever is earlier.

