7 DISCONTINUATION OF STUDY INTERVENTION AND PARTICIPANT DISCONTINUATION/WITHDRAWAL

7.1 DISCONTINUATION OF STUDY INTERVENTION

The IMP should be continued whenever possible. In case the IMP is stopped, it should be determined whether the stop can be made temporarily; permanent IMP discontinuation should be a last resort. Any IMP discontinuation should be fully documented in the e-CRF. In any case, the participant should remain in the study as long as possible.

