7.1.1 Permanent discontinuation

In rare instances, it may be necessary for a participant to permanently discontinue study intervention. If study intervention is permanently discontinued, the participant will remain in the study to be evaluated for the assessments planned for the EOT/EOS Visit, with the exception of the CT scan. See the SoA ([Section 1.3](#)) for data to be collected at the time of discontinuation of study intervention and follow-up and for any further evaluations that need to be completed.

Participants must be withdrawn from the study (ie, from any further IMP or study procedure) for the following reasons:

- At their own request or at the request of their LAR (an individual or judicial or other body authorized under applicable law to consent on behalf of a prospective participant to the participant's participation in the procedures involved in the research)
- If, in the Investigator's opinion, continuation in the study would be detrimental to the participant's well-being
- In case of surgery for NP
- At the specific request of the Sponsor
- In the event of a critical protocol deviation, at the request of the Investigator or the Sponsor
- In the event of an anaphylactic systemic allergic reaction that is related to IMP and that requires treatment
- In the event that the participant is diagnosed with a malignancy during the study, excluding carcinoma in situ of the cervix or squamous or basal cell
- Pregnancy
- Any opportunistic infection, such as TB or other infections whose nature or course may suggest an immunocompromised status (refer to Appendix 9 [[Section 10.9](#)])
- Met liver chemistry stopping criteria ([Section 7.1.2](#))

Handling of participants after permanent intervention discontinuation

Participants will be followed up according to the study procedures specified in this protocol up to the scheduled date of study completion or up to recovery or stabilization of any AE to be followed up as specified in this protocol, whichever comes last.

If possible, and after the permanent discontinuation of intervention, the participants will be assessed as soon as possible using the procedures normally planned for the EOT/EOS Visit (refer to SoA [[Section 1.3](#)]).

All cases of permanent intervention discontinuation must be recorded by the Investigator on the appropriate pages of the e-CRF when considered as confirmed.

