9.3.1 General considerations

The baseline value is defined generally as the last available value before first IMP administration.

The observation period will be divided into 2 segments:

- The **pre-treatment period** is defined as the period up to first IMP administration.
- The **treatment-emergent period** is defined as the period from the first IMP administration to the last visit in the study.

Dose regimen groups in the extension term after Week 24 will be defined as follows:

- 300 mg q2w group: participants who were administered at least 1 dose of the 300 mg q2w regimen and never experienced q4w administration during the extension term after Week 24
- 300 mg q4w group: participants who were administered at least 1 dose of the 300 mg q4w regimen during the extension term after Week 24

During the treatment term, including efficacy variable after Week 24, continuous variables and binary variables for efficacy by each visit will be summarized using descriptive statistics and frequency table in both the PP and mITT populations.

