### 5.2 APPENDIX 2 CHANGES TO PROTOCOL-PLANNED ANALYSES

Protocol Version	Approval Date	Changes	Rationale
1	11-May-2021	4.1 GENERAL CONSIDERATIONS	This is to prevent the case that patient discontinues treatment very

Protocol Version	Approval Date	Changes	Rationale
		
Observation period
 
 
The treatment-emergent period is defined as the period from the first IMP administration to the last visit in the study or the date of treatment discontinuation if discontinued from the study, whichever is earlier.
 
	
early, but have a EOS conducted, for example, 24 weeks after the last IMP.

		
4.1 GENERAL CONSIDERATIONS
 
Rescue
 
Participants who have undergone surgery or received SCS for any reasons, <del>and/or received selected prohibited medications</del> are considered rescued. NP surgery and SCS use will be determined by the corresponding eCRF pages, <del>while selected prohibited medications will be determined based on corresponding WHODD code in EFC14280.</del>
 
The date of rescue will be the earliest date of having undergone surgery or received SCS for any reason, <del>and/or received selected prohibited medications.</del>
 
And delete "selected prohibited medications" in the sections related to changes to the above definitions.
	
For the purpose of consistency with EFC14280, it focus the following data handling.
 
 
only surgery for NP or receive SCS triggers non-responder imputation
 
rescue treatment define as undergone surgery or received SCS
 

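### SAP 4.1 ends the treatment-emergent period at an undefined discontinuation date of unclear scope, and laboratory values after that date have no place in the PCSA and liver summaries

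*SAP*

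**What the plan says.** **The window.** In Protocol 9.3.1 the treatment-emergent period "is defined as the period from the first IMP administration to the last visit in the study". SAP 4.1 (Observation period) runs it from the first dose "to the last visit in the study or the date of treatment discontinuation if discontinued from the study, whichever is earlier". SAP 5.2 lists this as a change; its reason is the patient who stops treatment very "early, but have a EOS conducted, for example, 24 weeks after the last IMP".

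**Related dates.** SAP 5.4.4 defines the last-dose date, but for treatment duration only. SAP 4.7.1 adds 14 days (q2w) or 28 days (q4w) after the last dose, for exposure only.

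**What uses the window.** TEAE incidence is a secondary safety endpoint. SAP 4.7.3.1 restricts PCSA incidence and, if produced, the plot of peak ALT against peak bilirubin to the treatment-emergent period. The combined ALT and bilirubin criterion in Table 11 must be met inside one *treatment phase*, a term the SAP does not define. SAP 4.7.2 and Table 8 give later adverse events a post-treatment category and table.

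**After a stop.** Protocol 7.1 says: "In any case, the participant should remain in the study as long as possible". Protocol 7.1.1 adds that, if possible, "the participants will be assessed as soon as possible using the procedures normally planned for the EOT/EOS Visit", and that "All cases of permanent intervention discontinuation must be recorded by the Investigator on the appropriate pages of the e-CRF when considered as confirmed". The same section also states: "Participants must be withdrawn from the study (ie, from any further IMP or study procedure) for the following reasons"; that list includes "Met liver chemistry stopping criteria". Protocol Appendix 5 asks for repeated liver tests once IMP has been stopped for raised ALT.

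**The concern.** The rule leaves two choices to the programmer. The date could be the last dose or a later decision. The scope could be only those who leave the study, as the wording has it, or everyone who stops treatment early, as the rationale implies. Two competent programmers could give the same early stopper different windows and so different TEAE flags.

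The change was also not carried through to laboratory data. An adverse event after the cut moves to another table. A laboratory value after the cut goes to no planned abnormality summary. The values most likely to be dated after a stop are the EOT/EOS sample and the liver follow-up that the protocol asks sites to obtain. A bilirubin that first passes 2 x ULN in that follow-up would not be paired with the earlier ALT.

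**Working it through.** The plan gives no figure for this point. The only planning number needed is the sample size: 20 evaluable participants at 20% drop-out, 20/(1 - 0.20) = 25.

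**1. Date.** Protocol 7.1.3 makes a stop permanent once more than 2 doses are interrupted, that is, at the third missed dose.
- q2w: 3 x 14 = 42 days after the last dose.
- q4w: 3 x 28 = 84 days after the last dose.

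The two readings of the date can therefore differ by 42 or 84 days. A fixed tail of 14 or 28 days would fall short of such a decision date by 42 - 14 = 28 or 84 - 28 = 56 days. That is why the fix takes the later of the two.

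**2. Residual period.** If the date is the last dose, each q2w early stopper can lose up to 14 days against the SAP's own exposure tail. Assume 5 of 25 (the 20% drop-out) stop early on q2w: 5 x 14 = 70 participant-days. Against 25 x 168 = 4200 days this is 1.7%. If the five stop after one dose, the denominator is 20 x 168 + 5 x 14 = 3430, giving 2.0%. These are illustrations, not bounds; under a decision date the loss may be nil.

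**3. Scope.** In the SAP 5.2 example, the final visit comes 24 x 7 = 168 days after the last dose. If that participant stayed in the study, the literal text keeps those days as treatment-emergent and the rationale removes them.

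**4. Scheduled laboratory samples.** After baseline these fall at Weeks 8, 24 and 52 (Schedule of Activities; SAP Table 10). For a cut before Week 8, a later EOT/EOS sample is the only scheduled-type post-baseline sample (1 of 1). For a cut after the Week 8 sample and before Week 24 it is 1 of 2. This does not describe a liver-triggered stop, which needs a qualifying ALT before the stop.

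**5. Liver follow-up, assumed dates.** Take a q2w participant with last dose and first raised ALT on Day 57, retest on Day 60, tests every 48 hours to Day 74, then every 2 weeks to Day 130: 13 draws.

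| End of period | Draws inside |
|---|---|
| Last dose, Day 57 | 1 of 13 |
| Decision, Day 60 | 2 of 13 |
| Last dose + 14, Day 71 | 7 of 13 |
| Last visit, Day 364 (protocol; also literal SAP text if the participant stays in the study) | 13 of 13 |

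If the participant is withdrawn and the last visit comes early, the protocol's own window would close at that visit too.

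**6. Size per case.** 1/25 = 4 percentage points of a PCSA row.

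**The case against.** The change is declared with a reason, and SAP 4.6 rules out hypothesis testing, so only descriptive tables are touched. The rationale counts from the last dose and SAP 5.4.4 defines that date, which points to the last dose as the intended cut. The 14 and 28 days define exposure, not an adverse event window. The liver scenario is narrow: ALT and bilirubin are on the same panel, Appendix 5 mentions a 72-hour retest, and SAP 5.4.5 lets unscheduled values count for PCSA. The triggering ALT will normally already be in its row, so an omitted pair needs bilirubin to cross its threshold only after the cut.

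Most of this stands and limits the size. It does not supply the missing date or scope, and it does not give post-cut laboratory values a place.

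A reader might infer that every liver-triggered stop is cut whichever way the scope is read. The documents do not settle that. Protocol 7.1.1 says both that a participant who permanently stops IMP remains in the study for assessment and that meeting the liver criteria means withdrawal from it. If such a participant stays, the literal SAP text cuts nothing. These passages must be reconciled.

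A reader might also infer that a liver signal could go unreported. It would not: SAE and AESI reporting (Protocol 8.3.6, 10.2 note a and 10.3.2) applies regardless of this window, and later events have the post-treatment table.

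**Conclusion.** The concern holds as a minor defect in one SAP definition and its consequences. The cut-off date is undefined, no residual period is set, and the literal scope does not match the stated reason. For a participant who is cut, EOT/EOS and liver follow-up values dated after the cut are left out of the PCSA summaries and the ALT/bilirubin plot. The same holds for the ALT/bilirubin pair, provided *treatment phase* means the treatment-emergent period; no PCSA analysis is planned outside that period.

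The documents give no rate of liver-triggered stops, so the number affected is unknown and may be 0. One omitted case is 4 percentage points at n = 25. The gap is in the aggregate tables, not in case reporting. The day counts above rest on assumed dates and on reading the 20% drop-out as early treatment stops.

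**What to change.** 1. In SAP 4.1, define the discontinuation date. State whether the cut applies to everyone who permanently stops IMP or only to those withdrawn from the study, and align the wording with SAP 5.2. Reconcile the two statements in Protocol 7.1.1.
2. End the treatment-emergent period at the earlier of (i) the last visit and (ii) the later of the discontinuation date and last IMP + 14 days (q2w) or + 28 days (q4w). The last visit remains a cap, so the window can still close before the tail ends.
3. Keep the main PCSA table on that window. Also present PCSA, the ALT/bilirubin pair and the plot through the last available recorded value, with values after the window flagged as post-treatment.

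Two editorial points can go in at the same time: a post-treatment category for deaths, which are listed anyway, and a defined term in place of *on-treatment* in SAP 4.7.3.1 and 5.4.5.

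The cost is a text change, a rerun of the safety flags and one extra presentation. It uses recorded values only; Protocol 8.2.4 requires e-CRF entry of local results outside the protocol's tests only if they change management or are clinically significant. TEAE and PCSA rates may rise because of the residual period, or fall if the scope is widened to participants whom the literal text leaves uncut.
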